8.3.4 Reporting procedures

Any queries concerning adverse event reporting should be directed to the Study Co-ordinator.

All SAEs, whether expected or not, should be recorded on the relevant report form and followed up to resolution wherever possible. The CI (or delegated member of the SMG) should sign and date the SAE reporting form to acknowledge that they have performed the seriousness and causality assessments. SAEs should be reported from time of signature of informed consent, throughout the treatment period.

An SAE form is not considered as complete unless the following details are provided:

^{**} Note: Hospitalisation is defined as an inpatient admission, regardless of the length of stay, even if the hospitalisation is a precautionary measure for continued observation. Pre-planned hospitalisation e.g. for pre-existing conditions which have not worsened, or elective procedures, does not constitute an SAE.

^{***} Note: other events that may not result in death, are not life-threatening, or do not require hospitalisation, may be considered as an SAE when, based upon appropriate medical judgement, the event may jeopardise the participant and may require medical or surgical intervention to prevent one of the outcomes listed above.

- Full participant study number
- A Serious Adverse Event
- A completed assessment of the seriousness, and causality as performed by the CI (or another appropriately qualified individual on the delegation log).
- Only reports of related and unexpected SAEs should be submitted to the REC. These should be sent within 15 days of the CI becoming aware of the event.

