Participants will be asked to complete and send the signed consent within 24 hours of the meeting (if it is a working day). Participants will be asked to volunteer reasons for not consenting to participation if they choose. If the consent form is not received, the VIG-LD researcher will contact the potential participant three more times spread over a three week period. If a potential participant does not respond following the 3rd attempt they will not be contacted again.

As the parent is the participant in the present study, child assent will not be sought. However, consenting and eligible parents will be provided with a Child Notification Letter that explains the purpose and process of the study to children. The participant will be encouraged to go through the Child Notification Letter with their child. The letter includes information on how to contact the Study Coordinator if the child wishes to do so.

A separate consent form will be obtained for those who will participate in the process evaluation interviews; these will be both clinical service staff and parents. For this part of the study, a separate Participant Information Sheet and Consent form are available

Due to the aims and context of the research, monitoring of participants' capacity will not be undertaken. After consent, continued capacity will be assumed. However, help resources will be available through their clinical team should a participant require support due to loss of capacity.

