8.3 Safety Reporting

In the unlikely event that any Serious Adverse Events (SAEs) related to the intervention or research procedures should occur, the CI is responsible for ensuring that all staff involved in this study are familiar with the content of this section. Cis are responsible for notifying the Study Co-ordinator and CI. All SAEs must be reported immediately (and within 24 hours of knowledge of the event) to the sponsor by the study team. SAEs will be assessed at all follow-up time points, and intervention delivery staff will be trained to report these directly to the study team at any point during the study. Rates of SAEs by study arm will be reported to the TSC, and if required, to the REC. Additional information about the potential harm of the intervention will be collected through qualitative interviews with all stakeholders.

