8.3.1 Definitions

Term	Definition
Adverse Event (AE)	Any untoward medical occurrence in a participant administered an intervention which are not necessarily caused by or related to the VIG.
Serious Adverse Event (SAE)	 Any adverse event that - Results in death Is life-threatening* Required hospitalisation or prolongation of existing hospitalisation** Results in persistent or significant disability or incapacity Consists of a congenital anomaly or birth defect Other medically important condition***

^{*}Note: The term 'life-threatening' in the definition of serious refers to an event in which the study participant was at risk of death at the time of the event or it is suspected that used or continued used of the product would result in the participants death; it does not refer to an event which hypothetically might have caused death if it were more severe.

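### Section 8.3 gives conflicting rules on whose SAEs count, which SAEs, and until when, so the by-arm rates sent to the TSC could rest on unequal capture

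*Protocol*

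**What the plan says.** The safety rules are spread over several parts of the protocol.

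- **Timing and use (8.3).** "SAEs will be assessed at all follow-up time points, and intervention delivery staff will be trained to report these directly to the study team", and staff may do so at any time while the study runs. "Rates of SAEs by study arm will be reported to the TSC, and if required, to the REC". Section 5 (Questionnaires) places the follow-ups at 3 and 6 months after randomisation.
- **Window (8.3.4).** "SAEs should be reported from time of signature of informed consent, throughout the treatment period".
- **Treatment length (4.3).** VIG lasts at most 12 weeks. No treatment period is given for TAU.
- **Definition (8.3.1).** An adverse event is "Any untoward medical occurrence in a participant administered an intervention which are not necessarily caused by or related to the VIG". An SAE is an adverse event that meets a seriousness criterion, so it inherits this wording.
- **Scope.** 8.3 opens: "In the unlikely event that any Serious Adverse Events (SAEs) related to the intervention or research procedures should occur". Section 8.3.4 asks for every SAE, expected or not, to be recorded.
- **Who the participant is (7.3.2).** "As the parent is the participant in the present study, child assent will not be sought".
- **Schedule (Appendix 2).** No SAE item appears at any time point.

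**The concern.** These rules cannot all be followed at once. An SAE that happened in month 5 and comes to light at the 6-month contact has to be assessed under 8.3, yet for a VIG parent it lies outside the window in 8.3.4. For a TAU parent, nobody can say whether it lies inside, because no treatment period is defined. The definition in 8.3.1 turns on having been given an intervention, whereas the output promised in 8.3 is a rate for each randomised arm.

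The by-arm SAE rates are the quantitative safety data promised to the TSC, the independent oversight body. Researchers, therapists and sites could each comply with a different section and collect different events. With about 25 parents per arm, one or two events captured in one arm but not in the other would set the apparent picture.

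**Working it through.** The protocol gives no SAE risk or expected count, so there is no figure of its own to reproduce. The check sets the sections side by side and sizes the gap in the window.

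**1. Side by side**

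| Question | One rule | Another rule |
|---|---|---|
| When does reporting end? | 8.3: assessed at 3 and 6 months; staff reports at any time | 8.3.4: end of the treatment period (12 weeks at most for VIG, undefined for TAU) |
| Who is covered? | 8.3: rates by arm, hence both arms; 8.3.4: from consent, hence before randomisation | 8.3.1: a participant who has been given an intervention |
| Which SAEs? | 8.3, opening: those related to the intervention or the research | 8.3.4: all |
| Parent or child? | 7.3.2: the participant is the parent | No SAE section mentions the child |
| Which sources? | 8.3: follow-up assessment, in both arms | 8.3: intervention delivery staff, clearly available only for VIG |

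The second row also holds a conflict between 8.3.4 and 8.3.1: at consent nobody has yet been given the trial intervention.

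**2. Size of the window gap**

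Inputs: treatment of at most 12 weeks (4.3); follow-up of 6 months, taken as 26 weeks (section 5). The protocol does not fix when VIG starts. Let it start *w* weeks after randomisation and run a full 12 weeks.

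Weeks outside the 8.3.4 window = 26 − (12 + *w*) = 14 − *w*.

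- *w* = 0: 14/26 = 54%.
- *w* = 4 (an assumption): 10/26 = 38%.
- *w* = 0, with the 6-month contact at the end of its 3-week completion window (week 29): 17/29 = 59%.

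Twelve weeks is a ceiling, so a shorter course would leave more time outside the window.

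**3. What unequal windows could do**

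Assume 25 per arm, the same 6-month risk *r* in both arms, and a constant hazard. Suppose VIG were captured only to week 12 and TAU to week 26. The expected number of participants with an SAE is 25 × [1 − (1 − *r*)^(12/26)] in VIG and 25 × *r* in TAU.

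| Assumed *r* | VIG, to week 12 | TAU, to week 26 | Ratio |
|---|---|---|---|
| 5% | 0.58 | 1.25 | 0.47 |
| 10% | 1.19 | 2.50 | 0.47 |
| 20% | 2.45 | 5.00 | 0.49 |

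Equal true risk would look like roughly a halving in the VIG arm. The extra reporting by VIG staff pushes the other way, so the direction of any net distortion cannot be known in advance.

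**The case against.** The strongest defence is that 8.3 is the wider rule and can govern. It has both arms assessed at 3 and 6 months, and 8.3.4 does not say that nothing after treatment may be reported. On that reading the windows are equal and only loose wording remains. This is a fair reading, but nothing in the protocol says that 8.3 takes precedence, and 8.3.4 is the section headed as the reporting procedure. The extra VIG staff source remains on either reading.

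Several stronger conclusions are tempting and do not hold.

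- **The TAU count is zero by definition.** 8.3 requires a rate for each arm, 8.3.4 starts at consent, 8.3.1 itself distinguishes an intervention from VIG, and 4.3 also uses the word intervention for usual support. What remains is a literal gap for a TAU parent who has received nothing, which is possible because 7.1 recruits from waiting lists.
- **The arms will be formally compared, and the comparison is invalid.** The protocol says that rates are reported by arm. It plans no test.
- **There will be no data on harm to the child.** The DBC2 and the service-use interview are collected in both arms at baseline and 6 months, 8.1 covers safeguarding disclosures, and 8.3 adds interviews about harm. These may reveal some child events, but none of them is SAE reporting and none feeds the by-arm rate.
- **More than half of follow-up goes unreported.** The 54% needs a start at randomisation and needs 8.3.4 to override 8.3.

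Two further points stand. The missing row in Appendix 2 is weak evidence alone, since the appendix is a summary. And SAEs are neither a feasibility objective nor a progression criterion. With 25 per arm and no events, the one-sided 95% upper limit is still 1 − 0.05^(1/25) = 11%, so even consistent capture would give limited reassurance.

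**Conclusion.** The point holds as a contradiction within the protocol's own safety rules on the end of the reporting window, the population, and related versus all SAEs. Two gaps go with it: no statement on whether events in the index child count, and a reporting source that only the VIG arm clearly has.

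The window conflict concerns up to about 14 of 26 weeks (54%) for a full 12-week course that starts at randomisation, or about 10 weeks (38%) with an assumed 4-week delay. Both figures apply only if 8.3.4 is followed in preference to 8.3. The roughly two-fold distortion is an illustration that rests on assumed risks, a constant hazard and unequal windows between arms.

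Non-comparable rates are therefore a risk and not a certainty. The point does not touch the primary feasibility outcomes. It should still be put right, because these rules are fixed in the protocol itself and aligning them is cheap.

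**What to change.** Amend 8.3, 8.3.1, 8.3.4 and Appendix 2 together:

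1. Set one reporting window that applies equally to both arms and matches the 3- and 6-month assessments already in 8.3.
2. Reword the definition in 8.3.1 so that it covers every randomised participant, and make it agree with reporting from consent.
3. State one scope, related SAEs or all SAEs, in both 8.3 and 8.3.4.
4. State whether events in the index child count as SAEs.
5. Show the same SAE enquiry for both arms at 3 and 6 months in Appendix 2.
6. Report SAEs by source, so that events known only through VIG staff can be identified. Do not restrict the by-arm rate to parents who answer the survey: the retention criterion tolerates up to about 30% loss at 6 months, and a parent who has had a serious event may be among those who do not respond.

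The cost is a protocol amendment, one item added to existing contacts, and a few more SAE forms to process.

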4.3 Intervention

During VIG, the therapist meets with the parent to take a short video of the parent interacting with the child. This first meeting lasts about 20 minutes. At the second meeting (the week after), the parent and the therapist view select moments of the video, with a focus on moments when the interaction between parent and child is 'better than usual'. The therapist gently guides the parent to identify these moments and to identify how the parent's own behaviour contributes to successful and positive interactions. This second meeting is called shared review and lasts 40 minutes. The two meetings are called one VIG cycle. Three VIG cycles will be offered (standard practice), with an option for up to 2 additional cycles if the therapist or parent requests. An introductory and revision meeting take place around the cycles. The total maximum length of the intervention is 12 weeks.

Meetings typically take place in the parent's house or the clinic. When VIG happens remotely meetings take place over Teams or Zoom. For the purposes of this study, sites are being asked to offer VIG primarily remotely. However, if both the therapist and the parent consider a face to face meeting necessary to make the intervention more accessible, the first meeting for capturing the video (half of the 1st cycle) may take place face to face. Parents in the VIG group would also receive any other face-to-face or remote support made available by CAMHS during this 12-week period.

VIG is offered in few services so far, mostly face to face. Clinical services that offer VIG obtain consent from parents including for the video part which is integral to the mechanism of the intervention. Sites offering VIG and any other intervention as part of their usual support would be managing themselves the informed consent process with their clients. As an additional precaution, we added a clause in the study's consent form for participants in the VIG group to consent to being videotaped, in case any of the clinical sites do not have formal consenting processes for their interventions.

5 STUDY DESIGN and METHODS of DATA COLLECTION AND DATA ANALYSIS

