Study Design: A feasibility randomised controlled trial of 50 parents allocated on a 1:1 basis into intervention or treatment as usual (TAU), with an embedded process evaluation. We will collect service use data for cost comparison in a parallel feasibility economic evaluation. This will be conducted by a series of questionnaires and interviews.

Randomisation

Randomization will take place after participants have consented to the study and have had their eligibility confirmed by the screening process. Participants will be randomized on a 1:1 basis to the two study arms (VIG+ treatment as usual vs treatment as usual). The randomisation will be performed by the study statistician at the Cardiff Centre for Trials research.

Data collection methods:

From study participants:

- Interviews: Parents will be interviewed to determine eligibility to be included in the study; in addition to a few questions matching the inclusion/exclusion criteria, parents will be administered the Vineland-3 (Sparrow et al., 2016) to determine their child's overall adaptive skills score. Parents who enter the study will be interviewed to measure their levels of service use (CA-SUS; Byford et al., 1999) at baseline (before randomisation) and 6 months after randomisation.

 For the process evaluation, approximately 10 parents (five from each group) and approximately eight clinical staff (including VIG clinicians and Service Managers) will be interviewed at the 6-month follow up (semi-structured interviews) to investigate their experience of the study (intervention and evaluation acceptability); perceived effectiveness of VIG and implementation issues (VIG group only); barriers and facilitators for engagement with VIG (VIG group only), and contextual service factors that affect VIG delivery (VIG group only). Interviews will take place over the telephone or an online video platform (Teams or Zoom). Interviews will last between 30 minutes to one hour.

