- Questionnaires: Participants will be invited to complete questionnaires at baseline (before randomisation) and at two follow-up timepoints, 3- and 6-months postrandomisation: Parent-Child Relationship Scale (Pianta, 1992); parent mental health (PHQ-4; Kroenke et al., 2009); parenting (Alabama Parenting Questionnaire; Essau et al., 2006); parenting efficacy (Parenting Sense of Competence; Johnston & Mash, 2020); and child mental health (Developmental Behaviour Checklist-2 – DBC2 (not measured at 3-months); Gray et al., 2018). At 6-months, the survey will also include Vineland-3 items related to child socialisation and communication skills. At 3-months an additional question will measure the ways participants have been supported by specialist mental health services over the preceding 3-month period, so as to describe the content of Treatment as Usual (TAU) and VIG. Participants' satisfaction with specialist mental health services' input (both groups) will be measured using the 9-item 'Satisfaction with Care' sub-scale of the Experience of Service Questionnaire (ESQ; Brown et al., 2014). We envisage questionnaire completion to take place through an online survey link set up in Qualtrics; participants will also be offered a choice of completing the questionnaires offline (emailed a measure pack) or arranging a tele/video conference with the researcher to go through measures. Participants will be asked to complete the questionnaires within a 3-week window of either side of the follow-up date. Questionnaire completion will take up to an hour each time point.

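### Protocol sections 8.3 and 8.3.4 give different SAE windows, and the treatment period that closes one of them is undefined, with no length at all for the TAU arm

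*Protocol*

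**What the plan says.** Section 8.3.4 (Reporting procedures) opens and closes the reporting window: "SAEs should be reported from time of signature of informed consent, throughout the treatment period". It names no follow-up period.

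Section 8.3 (Safety Reporting) is wider in three ways:

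- On timing: "SAEs will be assessed at all follow-up time points". Section 5 places the questionnaires after baseline "at two follow-up timepoints, 3- and 6-months postrandomisation", so the last follow-up point is at 6 months.
- On staff: "intervention delivery staff will be trained to report these directly to the study team at any point during the study".
- On output: "Rates of SAEs by study arm will be reported to the TSC".

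The treatment period is not defined anywhere. Section 4.3 gives one length, for VIG: "The total maximum length of the intervention is 12 weeks". The only sentence that ties usual support to a period is about the intervention arm: "Parents in the VIG group would also receive any other face-to-face or remote support made available by CAMHS during this 12-week period". Under Randomisation in section 5, the arms are VIG plus TAU against TAU, allocated 1:1. No length of treatment is stated for TAU alone.

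**The concern.** A reporting window decides which events are collected at all. Section 8.3 implies that an SAE in month 5 is in scope. Section 8.3.4, read as written, implies that it is not, because the VIG course is over by then. A site or researcher following one section would act differently from one following the other.

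For a parent randomised to TAU the rule in 8.3.4 cannot be applied without interpretation, because the event that closes the window is not defined. Yet the protocol promises SAE rates by arm, and such a rate needs a stated period of observation that is common to both arms.

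At stake are the completeness of safety data after the VIG course and the meaning of the by-arm rates that the TSC will see. The protocol's own rationale asks for outcomes in the medium term, at 6 months, so a safety window that ends with the course sits poorly with it. A statistical analysis plan would not normally repair this: the rule governs collection, and events that were never reported cannot be analysed later.

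**Working it through.** The protocol gives no expected SAE number or rate, so there is no figure to reproduce. The check is a comparison of the sections and some time arithmetic.

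**The two rules side by side**

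| | Section 8.3.4 | Section 8.3 |
|---|---|---|
| Window opens | Signature of consent | Not stated |
| Window closes | End of an undefined treatment period | Last follow-up point, 6 months (assessments); end of study (reports by delivery staff) |
| Length for VIG + TAU | 12 weeks at most after the start of VIG, if the treatment period means the course | To 6 months |
| Length for TAU | None given | To 6 months |

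**Does anything else settle it?**

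- The instruction in 8.3.4 to follow SAEs to resolution concerns events already recorded. It does not extend the window for new ones.
- The schedule in Appendix 2 has no SAE row at any visit, so it does not confirm the assessments described in 8.3.
- The AE definition in 8.3.1 refers to a participant who has been given an intervention. That fits the TAU arm poorly and does not supply a window for it.
- Continuous reporting under 8.3 is assigned to intervention delivery staff, so it does not clearly reach parents in the TAU arm.

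**Uncovered time in the VIG arm if 8.3.4 is applied literally**

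Inputs: the VIG maximum of 12 weeks = 12 × 7 = 84 days (section 4.3); last follow-up at 6 months = 6 × 365.25/12 = 182.6 days, about 26 weeks (section 5). The delay from randomisation to the start of VIG is not stated, so a range is assumed.

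Uncovered days = 182.6 − (84 + delay). Share = uncovered days / 182.6.

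| Assumed start delay | Uncovered days | Weeks | Share of 6 months |
|---|---|---|---|
| 0 | 182.6 − 84 = 98.6 | about 14 | 54% |
| 2 weeks (14 days) | 182.6 − 98 = 84.6 | about 12 | 46% |
| 4 weeks (28 days) | 182.6 − 112 = 70.6 | about 10 | 39% |
| 8 weeks (56 days) | 182.6 − 140 = 42.6 | about 6 | 23% |

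These rows assume a course of the full 12 weeks. A shorter course with the same start date leaves a longer uncovered period. No equivalent table can be made for TAU, because its window has no stated end.

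**The case against.** The strongest reply is that the sections can be read together. Section 8.3 requires all SAEs to go to the sponsor within 24 hours of the study team learning of them, and 8.3.4 itself begins by requiring every SAE to be recorded. Nowhere does the protocol say that an SAE after treatment must not be reported. On that reading, an SAE found at the 6-month contact is assessed and reported in either arm. This stands to the extent that the loss of late events is conditional: it occurs only if the sentence in 8.3.4 overrides 8.3. Equating the treatment period with the VIG course is also an inference, though from the only length given. It does not remove the conflict, because the one sentence that states a window names an end point earlier than 6 months.

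Three stronger readings are tempting, and the protocol does not support them.

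- A reader might infer that the arms would be counted over different times and that VIG would therefore look safer. That needs usual care to count as treatment up to 6 months in the TAU arm but not in the VIG plus TAU arm. Section 6 offers TAU to both groups, and nothing in the protocol makes that distinction.
- A reader might see a defect in opening the window at consent, since many consenting families may never be randomised. Opening at consent is a reasonable choice, and events before randomisation need not enter by-arm rates. The size of that group is also unsettled: the planning figure of 100 families is described as eligible under Recruitment in section 5, but as consenting in the progression criteria and section 7.2.1.
- A reader might infer that the SAE form lacks an onset date, because the completeness list in 8.3.4 does not name one. The form is not shown, so this cannot be checked.

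It is also fair to say that a 50-parent feasibility trial will support no between-arm safety conclusion, whatever the window, and that harms are explored in the interviews too. This bears on severity, not on whether the text is consistent.

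**Conclusion.** The inconsistency holds. Two safety sections of one protocol give different SAE windows, the term that closes the narrower one is undefined, and it has no stated meaning for TAU alone. This rests on the text and on no assumption.

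The size is conditional. If 8.3.4 is applied literally and the treatment period is the VIG course, up to about 14 of 26 weeks after randomisation fall outside reporting in the VIG arm when VIG starts at randomisation. With assumed start delays of 2, 4 or 8 weeks the figure is about 12, 10 or 6 weeks. If 8.3 is applied, nothing up to 6 months is lost. No bias in a particular direction between the arms can be claimed.

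The sections should be reconciled, but this is not among the most serious problems a plan can have. Safety is not one of the three primary feasibility outcomes (recruitment, retention and VIG completion) on which progression depends.

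**What to change.** Replace the window sentence in section 8.3.4 with one rule for both arms, for example: SAEs are reported from signature of consent until the 6-month assessment or, if that is not completed, until its window closes, in the same way in both arms. Section 5 already sets that window at 3 weeks either side of the follow-up date.

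Add to section 8.3: by-arm rates count events with onset from randomisation to 6 months, and events between consent and randomisation are listed separately.

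The cost is a few sentences in the protocol and a few more SAE forms for events between the end of the VIG course and 6 months. No treatment or visit changes.
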